#### 11.1.5.1. ATG-010 Dose Reduction due to Decreased Glomerular Filtration Rate

ATG-010 is not mainly eliminated by kidney; therefore, there is no need to change the dose of ATG-010 in the presence of kidney dysfunction; however, creatinine clearance must be  $>20$  mL/min, otherwise ATG-010 plus low-dose dexamethasone treatment cannot be initiated. If creatinine clearance is decreased during the treatment period and is considered unrelated to ATG-010, the dose of ATG-010 may be maintained, but patient's condition must be closely monitored. If creatinine clearance is decreased to  $< 20$  mL/min, it is considered to be related to ATG-010, and then the dose of ATG-010 should be lowered by 1 level. If creatinine clearance is restored to  $>20$  mL/min and stays at this level for 4 weeks, the dose of ATG-010 can be restored to the previous level. If dialysis is given during the ATG-010 plus low-dose dexamethasone treatment period, ATG-010 plus low-dose dexamethasone must be given after dialysis.

#### 11.1.5.2. Adjustment of ATG-010 Dose in the Presence of Infection

Any patient with grade  $\geq 3$  infection should interrupt ATG-010, until the infection is clinically resolved or the patient is clinically stable, and then ATG-010 administration can be re-initiated by lowering 1 dose level. If the Investigator assesses that the infection is unrelated to the study drug and decide the administration of study drug can be continued, this decision should be made per discussion with the Sponsor's Medical Monitor.

Dexamethasone should be adjusted according to the guidelines of the medical institution, with

adrenal suppression being taken into account. Missed doses shall not be made up. While re-initiating ATG-010 regimen, patients can continue long-term treatment with antibiotics or other antimicrobial agents per the Investigator's discretion.

#### **11.1.5.3. Cases not Requiring ATG-010 Dose Reduction**

Below are exceptional cases to the dose modification guidelines. There is no need to interrupt ATG-010 in the following cases:

- Any grade of alopecia
- Electrolyte or serum analyte (e.g., urate) abnormalities that can be reversed by standard intervention

#### **11.1.5.4. Dose Modification to Missed Dose or Vomiting**

Note: A maximum of 2 ATG-010 doses can be given per week.

##### **Missed Dose**

**If a dose is missed**, the treatment schedule of the week should be modified to adapt to the 2 doses of the week, and 2 consecutive doses should be at least 36 hours apart.

**If this dose must be skipped** (for example, per attending doctor's advice), the next dose should be taken according to the treatment schedule. The dosing interval should not be less than 36 hours, and all missed doses and delayed doses should be recorded.

##### **Vomited Dose**

If vomiting occurs  $\leq$  1 hour after dosing, another dose should be taken. If vomiting occurs  $>$  1 hour after dosing, the patient will be regarded as having taken a full dose.

#### **11.2. Study Drug Storage**

ATG-010 tablets should be stored in a safe area with access only to the study site personnel pharmacists or designees, at a temperature no more than 30°C (i.e., room temperature or refrigerating temperature). Room temperature storage is preferred. The tablets should not be frozen. Study sites need to record the temperature of the storage place for the study drugs.

ATG-010 tablets (20 mg) are supplied in plastic blister packs with an aluminum foil lid. For detailed information on the preparation, storage, stability, and administration of ATG-010, see Appendix 4.

Dexamethasone tablets should be stored according to the suggestions in the package inserts.

#### **11.3. Study drug Accountability**

The Investigator or designee must record the count and dispensing of study treatment drugs in the drug record log. Patients need to return all unused study treatment drugs and packages on a regular basis, at the end of study, or upon discontinuation of study treatment. During study site visits and at the completion of study, Clinical Research Associate (CRA) should check the drug count periodically.

During the course of the study and at study close out, the Investigator should return all used and

unused study treatment drugs as well as a copy of the completed drug record log to the Sponsor.

ATG-010 shall not be used for any purposes outside the scope of this study protocol, nor shall it be transferred or licensed to any party not participating in this clinical study. The data of ATG-010 are proprietary confidential information, and the Investigator should keep it in this way.

The Investigator or a responsible party designated by the Investigator must carefully record the inventory and disposition of unused materials.

Before being used or returned to Antengene or destroyed by the designee, all drug supplies provided by Antengene must be stored in an appropriate safe place with limited access. The drug supplies must be counted and verified at the study site before being returned. Study sites need to maintain a temperature log of the storage place for the study drugs.

#### **11.4. Concomitant therapies**

##### **11.4.1. 5-HT3 Antagonists Required**

Unless contraindicated, all patients should receive 5-hydroxytryptamine (5-HT3) antagonists (e.g., palonosetron or equivalent) before the first dose of ATG-010 to minimize nausea. Alternative antiemetic agents may be used if the patient does not tolerate 5-HT3 antagonists.

##### **11.4.2. Supportive Care**

During the period of participation in this clinical trial, supportive measures should be taken to ensure the best medical care for patients. It is advised that patients maintain sufficient intake of liquids and calories during the course of treatment. Intravenous fluids therapy may be considered for patients at risk of dehydration. Patients will also receive blood product transfusions, antimicrobials, and growth factors including granulocyte colony-stimulating factors (for neutropenia), erythropoietins (for anemia,) and/or platelet-stimulating factors (for thrombocytopenia) as the best supportive treatment.

In addition to dexamethasone included in the standard treatment plan and required 5-HT3 prophylaxis (Section 11.4.1), the following supportive care (including anti-nausea/antiemetic therapy), antacids (proton pump inhibitors [PPIs] and/or H2 blockers), and other therapies may also be given:

- Appetite stimulants: Megestrol acetate, at a dose of 80-400 mg per day.
- Centrally acting preparations: Olanzapine, 2.5-5.0 mg per night by oral is recommended.
- Neurokinin 1 receptor antagonists (NK1R antagonists): Aprepitant or equivalent may be considered, covering selected patients with severe nausea and vomiting.

Additional anti-nausea and anti-anorexia agents may be given as needed (per National Comprehensive Cancer Network® [NCCN] Clinical Practice Guidelines® for Antiemesis, NCCN Clinical Practice Guidelines® for Palliative Care and Chinese Expert Consensus on Prevention and Treatment of Nausea and Vomiting Related to Anti-Cancer Drug Treatment (2019 version)).

##### **11.4.3. Infection**

In patients with fever or other signs of systemic infection, appropriate broad-spectrum intravenous

antibiotics and antifungals should be initiated immediately.

#### 11.4.3.1. Other Glucocorticoid Side Effects

The management of common glucocorticoid side effects has been detailedly recorded. In this study, it is strongly recommended to actively use proton pump inhibitors (PPIs), anti-hypertensives, and other preparations, so that the combined use of dexamethasone plus ATG-010 can be continued.

Patients with documented osteopenia or osteoporosis should continue to use dexamethasone with ATG-010 according to the requirements of this study. Standard precautionary measures should be formulated, for example, use of bisphosphonates, unless contraindicated.

#### 11.4.4. Concomitant Medications and Therapies

Concomitant medications refer to any prescription drugs or over-the-counter preparations for prophylactic or therapeutic purposes, including vitamins, dietary supplements, over-the-counter medications, and oral herbal preparations. Patients can continue taking baselines drugs previously taken. All concomitant medications must be recorded in the eCRF (except for diagnostic or surgical preparations). Any diagnostic, therapeutic or surgical procedures performed during the study period should be recorded, including the dates, operating procedures, and any clinical findings (if applicable).

##### 11.4.4.1. Concomitant Medications Allowed

Concomitant medications can be used for managing symptoms, AEs, and intermittent diseases, and if medically necessary, can be used as standard of care. Medications for treating concomitant diseases such as diabetes mellitus, hypertension, and etc. are allowed.

#### 11.4.5. Restricted Medications

*Medication:* Theoretically, ATG-010 interacts with glutathione (GSH); therefore, the use of acetaminophen (Paracetamol) plus ATG-010 was limited in previous ATG-010 studies. However, no significant clinical or laboratory abnormalities were found by the ongoing clinical safety evaluation on the combined use of these drugs [up to 1 g of acetaminophen and up to 55 mg/m^2 (about 80-100 mg) of ATG-010]. Accordingly, there is no longer any restrictions on the combined use of acetaminophen or acetaminophen-containing drug with ATG-010, except that acetaminophen must not exceed a total daily dose of 1 g on the dosing days of ATG-010.

*Diet:* There is no dietary restriction in this study. Patients should maintain sufficient intake of calories and liquids.

#### 11.4.6. Prohibited Medicines

*Concurrent therapy:* Concurrent therapy with any anticancer therapy drugs other than the study drugs is not allowed. Other investigational drugs shall not be used during the study. Any immunosuppressant use during the study period must be confirmed by the Medical Monitor.

*Medication:* In this study, patients shall not use any drugs containing glutathione (GSH), S-adenosyl methionine (SAM), or N-acetylcysteine (NAC), since they may

promote ATG-010 metabolism. See Appendix 5 for the list of representative drugs. In this study, patients must report all prescription and over-the-counter drugs to the doctor.

#### 11.4.7. Contraception Requirements

During the study period, patients shall not get pregnant or father a child, since the study treatment in this study will affect the fetus. Women shall not breastfeed during the study period. Patients should be aware of that contraceptive measures must be taken while on the study; this is extremely important. Female patients of childbearing potential must agree to use 2 contraceptive methods (1 highly effective contraceptive method and 1 effective contraceptive method) and have a negative serum pregnancy test at Screening. Male patients, if sexually active with females of childbearing potential, must adopt an effective barrier method of contraception. Highly effective contraceptive methods include:

1. Hormonal contraceptives (e.g., compound oral contraceptives, contraceptive patch, vaginal ring, injectable contraceptives, and implantable contraceptives)
2. Contraceptive ring or intrauterine device
3. Vasectomy or tubal ligation

Effective contraceptive methods include:

1. Barrier contraception (e.g., male condom, female condom, cervical cap, contraceptive diaphragm, and contraceptive sponge)

It should be particularly noted that,

- A barrier method of contraception itself alone cannot be used as highly effective contraception.
- Correct use of contraceptive diaphragm or cervical cap, including use of spermicide, is one kind of barrier method of contraception.
- Cervical cap and contraceptive sponge are not very effective in parous women.
- Use of spermicide alone is not an appropriate barrier method of contraception.
- Male condom plus cervical cap, contraceptive diaphragm or sponge with spermicide (double-barrier method of contraception) is acceptable, but not a highly effective contraception.
- Male condom and female condom shall not be used simultaneously, otherwise they may be torn up or damaged.

In other words, the following contraceptive requirements should be met:

1. Permanently surgically sterilized or post-menopausal sex partner
2. Complete (real) sexual abstinence (when satisfying patient's preference and daily lifestyle) is an acceptable method of contraception. Note: Periodic abstinence (e.g., calendar method, ovulation period method, symptothermal method, and post-ovulatory contraception) and coitus interruptus are not acceptable.

Acceptable contraceptive methods must be explained to potential male and female patients. Patients must agree to use the contraceptive methods described above throughout the study period and for 3 months after the last dose of study treatment, otherwise they will not be eligible for participating in this study.

For more safety information about pregnancy, please see Section 4.31.

#### **11.4.8. Radiation Therapy**

If clinically indicated, palliative radiotherapy for non-target lesion(s) are permitted, however, the study drugs should be held for  $\geq 1$  day prior to initiation of palliative radiotherapy and  $\geq 1$  day after each dose of palliative radiotherapy. ATG-010 treatment shall not be terminated solely due to palliative radiotherapy.

#### **11.5. Treatment Compliance**

Investigator or other study personnel should supervise the study drug treatment administered in the study site and guide patients on study drug self-administration. Patients will be asked to bring their study drug packages at each visit, and their compliance with the study drug intake specified in the protocol will be checked by tablet count.

After discussing with the patient and drug counting staff, the study personnel will record the compliance of study drug. The Investigator or designee will assess the compliance of study drug and record it in the source documents. The date will be recorded according to the study drug schedule. The Investigator or designee will count the number of dispensed tablets against the number of tablets returned by patient. Any dose deviations and missed doses will be recorded in the eCRF and drug accountability log to confirm the corresponding reason.

## 12. Adverse Event

An AE is any untoward medical occurrence in a patient or clinical study subject administered with a certain pharmaceutical product, irrespective of its causal relationship with the treatment. An AE can therefore be any unfavorable and unintended sign (e.g. an abnormal laboratory finding), symptom, or disease temporally associated with the use of an investigational product, whether or not related to the investigational product.

It is expected that, clinically significant symptoms and signs associated with disease progression will be reported as AE; however, disease progression that is asymptomatic or confirmed by examinations only does not need to be reported as an AE.

All SAEs will be recorded since the subject signs the informed consent form. AEs will be recorded after the use of study drug till 30 days after the last dose. Any SAE learned by the Investigator at any time thereafter and suspected to be related to the study drug will also be recorded.

Any abnormal laboratory finding or test result (e.g., PE, ECG, Echo, vital signs, etc.) occurring during treatment, if clinically significant (i.e., meeting any one or more of the following conditions), should be recorded as a single diagnosis on the AE page of the eCRF.

1. Is accompanied by clinical symptoms
2. Leads to a change of study drug (e.g., dose modification, interruption, or permanent discontinuation)
3. Requires a change of concomitant therapy (e.g., addition, interruption, termination, or any other changes of concomitant medications, therapies or treatment).

Investigator is responsible for recording all AEs occurring during the study period. Patients will be asked a non-directive question, for example, "Since our last inquiry/since the last visit, have you experienced any new symptoms or are there any changes in the symptoms?" AE should be reported on the corresponding page of the eCRF.

The actual grade and duration of AE should be reported.

The severity/intensity of AE will be graded based on subject's symptoms per current Common Terminology Criteria for Adverse Events (CTCAE, v4.03).

AEs that are not included in the CTCAE will be assessed according to the following criteria:

- Grade 1 = transient or mild discomfort; activity not limited; no medical intervention/therapy required;
- Grade 2 = mild-to-moderate or moderate limitation in activity, some assistance possibly required; no or minimal medical intervention/therapy required;
- Grade 3 = moderate to marked limitation in activity, some assistance usually required; medical intervention/therapy required, hospitalizations possible;
- Grade 4 = Life threatening - extreme limitation in activity, significant assistance required; significant medical intervention/therapy required, hospitalization or hospice care probable;
- Grade 5 = death - the event results in death.

The term "severe" is used to describe the severity of AE; the event itself may have little clinical significance (e.g., "severe" headache). This is different from "serious". The seriousness of AE is based on its outcome and is usually associated with events posing a threat to patient's life or functions.

Investigator will make judgments on the correlation between AE and study drug, as shown in [Table 7](#) below.

**Table 7: Classification of AEs Listed Per Causal Relationship**

Not Related	The event is not temporally associated with the study treatment, or by providing any other drug, therapeutic intervention, or underlying disease that can fully explain the event, the assessment of causality rules out the possibility of a reasonable causal relationship.
Related	The temporal association between the event and study treatment constitutes a definite causal relationship, and compared to any other drug, therapeutic intervention, or underlying disease, the event may be more reasonably explained by the exposure to study treatment.

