#### 4.2.3. Clinical Safety Results

The most common TEAEs in the study were low-grade and reversible events and/or responded to the supportive care and dose modification. The most common TEAEs (≥35%) included nausea (65.1%, 1352/2076 cases), fatigue (57.9%, 1203/2076 cases), thrombocytopenia (52.1%, 1082/2076 cases), anorexia (MedDRA “decreased appetite”) (51.0%, 1058/2076 cases), anemia (42.3%, 879/2076 cases), vomiting (38.2%, 794/2076 cases), and diarrhea (36.0%, 747/2076 cases).

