#### 4.3. Potential Risk

On July 3, 2019, FDA granted accelerated approval to selinexor. Post-marketing experience will be provided in the periodic adverse drug reaction report. FDA approved selinexor in combination with dexamethasone for adult patients with RRMM who have received at least 4 lines of prior therapies and whose disease is refractory to at least 2 proteasome inhibitors, at least 2 immunomodulatory agents, and an anti-CD38 monoclonal antibody.

This study will continue to evaluate the efficacy and safety of selinexor plus dexamethasone in Chinese patients with RRMM. Measures will be taken to guarantee the safety of patients participating in this trial, including formulating strict inclusion and exclusion criteria and closely monitoring subjects’ AEs.

If a patient experiences an AE during the course of the clinical trial, the Investigator may adjust the study treatment according to the protocol. During the trial period, and within 30 days after the last dose of study treatment or prior to the initiation of another anti-cancer therapy, all AEs and serious adverse events (SAEs) will be recorded, whichever comes first.

The most common AEs possibly related to ATG-010 are nausea, fatigue, thrombocytopenia, anorexia, anemia, vomiting, and diarrhea. In fact, all these side effects can be effectively managed with the modified dose of the study drug and/or the supportive care initiated prior to the first dose. Overall, the most common laboratory abnormalities includ thrombocytopenia, hyponatremia, and decreased erythrocytes. The majority of these AEs were mild or moderate in severity. For more information,

please refer to the Investigator's Brochure.

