#### 13.3.6.1. Adverse Event

AEs will be coded per Medical Dictionary for Regulatory Activities (MedDRA) and presented in tables and listings per MedDRA System Organ Class (SOC) and Preferred Term (PT).

Events deemed to be treatment-emergent will be included in AE analysis, where "treatment-emergent" refers to any AE or exacerbation of a pre-existing disease that emerges or after the first dose of study treatment or within 30 days after last dose of study treatment, or any event that emerges prior to the end of study and is considered drug-related by the Investigator. AEs with partial dates available will be assessed using the existing date information to determine if they are treatment-emergent; AEs with dates completely missing will be assumed as treatment-emergent. No formal hypothesis testing will be performed on the incidence rates of AEs.

AEs will be summarized per patients' incidence rates; therefore, each patient will be counted only once for a given AE (Preferred Term) in any listing. The number and percentage of patients with any treatment-emergent adverse event (TEAE) will be summarized per treatment group, and stratified per SOC and Preferred Term. The number and percentage of patients with TEAE that is assessed as at least possibly related to treatment by the Investigator will also be listed. The number and percentage

of patients with any Grade  $\geq 3$  TEAE will be listed in the same way.

The Investigator will assess the causal relationship between an AE and the study drug as not related or related. If a patient experiences the same AE repeatedly, events with the highest severity and/or with a strong causal relationship with treatment will be used for the purpose of tabulations.

All SAEs reported will be listed.

All AEs (emerging during and after treatment) will be presented in the individual patient data listings and will be classified per treatment, patient, and study day. In addition, individual patient listings will be provided for the following events: deaths, SAEs, and AEs leading to withdrawal.

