Relapse from MRD Negative (to be used only if the endpoint is disease-free survival)	Any one or more of the following criteria: Loss of MRD negative state (evidence of clonal plasma cells on NGF or NGS, or positive imaging study for recurrence of myeloma); Reappearance of serum or urine M-protein by immunofixation or electrophoresis; Development of $\geq 5\%$ clonal plasma cells in the bone marrow; Appearance of any other sign of progression (i.e., new plasmacytoma, lytic bone lesion, or hypercalcemia)

Abbreviations: ASCT = autologous stem cell transplantation; CR = complete response; CRAB features: calcium elevation, kidney failure, anemia, lytic bone lesion; CT = computed tomography; DOR = duration of response; FDG = fluorodeoxyglucose; FLC = free light chain; hr = hour; Ig = immunoglobulin; IMWG = International Myeloma Working Group; MM = multiple myeloma; MR = minimal response; MRD = minimal residual disease; MRI = magnetic resonance imaging; NGF = next-generation flow cytometry; NGS = next-generation sequencing; PD = progressive disease; PET = positron emission tomography; PFS = progression-free survival; PR = partial response; sCR = stringent complete response; SD = stable disease; SPD = sum of products of two longest perpendicular diameters; TTP = time to progression; VGPR = very good partial response.

Source: [Kumar, 2016](#)

 All response categories require two consecutive assessments made at any time before the institution of any new therapy; for MRD there is no need for two consecutive assessments, but information on MRD after each treatment stage is recommended (e.g., after induction therapy, high-dose therapy/ASCT, consolidation, maintenance). MRD tests should be initiated only at the time of suspected CR. All categories of response and MRD require no known evidence of progressive or new bone lesions if radiographic studies were performed. However, radiographic studies are not required to satisfy these response requirements except for the requirement of FDG-PET if imaging MRD-negative status is reported.

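### Table 7 and Section 13.3.6.1 use inconsistent causality thresholds, so the related-TEAE table does not match its own label

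*Combined protocol and SAP*

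**What the plan says.** Section 12 states that the "Investigator will make judgments on the correlation between AE and study drug" and refers to Table 7 for the classification. Table 7 has two rows.

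- **Not Related** can be met in two ways. Either there is no link in time with treatment, or some other drug, intervention or disease accounts for the event in full, so that "the assessment of causality rules out the possibility of a reasonable causal relationship".
- **Related** has two conditions joined by *and*. The first is that "The temporal association between the event and study treatment constitutes a definite causal relationship". The second is that, set against the alternatives, "the event may be more reasonably explained by the exposure to study treatment".

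Section 13.3.6.1 repeats the two-level scale as the one the investigator will use. The same section plans to list patients with a "TEAE that is assessed as at least possibly related to treatment by the Investigator". When a patient has the same event more than once, it chooses the episode to tabulate by highest severity, by a strong relationship to treatment, or both.

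For events later than 30 days after the last dose, Section 12 records SAEs that are *suspected* to be related. Section 13.3.6.1 counts late events as treatment-emergent if they are *considered* drug-related.

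**The concern.** A two-level causality scale works only if every event falls in exactly one level and the tables use those levels. Here the two rows appear to leave a middle band without a category, and the analysis section names thresholds (possible, strong) that the scale cannot record.

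The trial is single-arm and multi-center, so there is no control rate against which to read the related-TEAE table. It rests on each investigator's attribution. If the written definition excludes events that the table says it counts, or if sites fill the gap in different ways, a reader of the clinical study report cannot tell what the related rate means. A later mapping in the SAP cannot repair this, because a middle level that was never recorded cannot be recovered.

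**Working it through.** No sample-size or power figure enters this point, and the plan gives no figure to reproduce. The check is a logical one on the definitions.

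**1. Inputs from Table 7.** For a given event let

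- T = associated in time with treatment
- F = another cause fully explains it, so a reasonable relationship is ruled out
- D = the relationship is definite
- M = treatment is the more reasonable explanation

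Then Not Related = (not T) or F, and Related = T and D and M.

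**2. Do the rows cover every event?**

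| T | F | D and M | Row met |
|---|---|---|---|
| no | – | – | Not Related |
| yes | yes | – | Not Related |
| yes | no | yes | Related |
| yes | no | no | none |

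The rows do not overlap in substance: an event that another cause fully explains cannot also be definitely due to the drug. They do not cover all cases, because the last line has no category.

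**3. Is the last line realistic?** Section 4.3 says that "The most common AEs possibly related to ATG-010 are nausea, fatigue, thrombocytopenia, anorexia, anemia, vomiting, and diarrhea". Appendix 3 lists among the signs of myeloma itself the "CRAB features: calcium elevation, kidney failure, anemia, lytic bone lesion". Take an on-treatment anemia that the myeloma explains only in part. T holds, F fails because the explanation is partial, and D fails because the relationship is not definite. Neither row applies, yet the investigator must enter one.

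**4. Effect on the table in Section 13.3.6.1.** Let d be the share of patients with at least one event that meets Related in full. Among the other patients, let m_p be the share with an event in the gap that is at least possibly related, and m_u the share whose gap events are all unlikely but not excluded. The table's label asks for d + m_p.

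- Related row applied literally: everything in the gap goes to Not Related, the table shows d, and the error is −m_p.
- Not Related row applied literally: everything in the gap goes to Related, the table shows d + m_p + m_u, and the error is +m_u.
- Investigators differ: the table shows some value between d and d + m_p + m_u, with no single threshold behind it.

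The documents give none of d, m_p or m_u. With the planned 82 patients, each patient who changes category moves a related rate by 1/82 = 0.0122, or 1.22 percentage points. That is a unit, not an estimate.

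**5. Repeated events.** Suppose a patient has a Grade 3 episode judged unrelated and a Grade 1 episode of the same term judged related. Selection by severity takes the first and selection by relationship takes the second. The rule permits either and does not say which table uses which.

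**6. What does not depend on the category.** The primary endpoint is IRC-assessed response. TEAE status up to 30 days after the last dose does not use causality, and all reported SAEs are listed. The Grade 3 or higher count asks for patients with any such event, which is naturally read at worst grade. AE rates are not formally tested.

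**The case against.** **The table can still be produced.** This is correct. The recorded item has two levels, so the programmer counts events coded Related. A reader might infer that the table is therefore meaningless or cannot be run, but the documents do not support that. The defect is that the count does not match its label and may vary between investigators.

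**The word definite may come from translation.** This is plausible. The document is marked as translated, and the hedged comparative wording of the second Related condition sits badly with a literal *definite*. The source text should be checked. Translation of that one word would not explain why Section 13.3.6.1 pairs a two-level scale with a possible-or-higher threshold and a strong-relationship rule.

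**The eCRF or the separate SAP may settle it.** Section 13.1.1 refers to an SAP for details, and neither it nor the eCRF was supplied. They may help. Investigators are nevertheless directed to Table 7.

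**Little rests on it.** In part this stands: the rates are descriptive. A reader might also infer that attribution is the only safety evidence in a trial without controls. That goes too far. Section 13.3.6.2 plans changes from baseline and CTCAE shift tables for laboratory values, including hematology, which do not use attribution.

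**Conclusion.** The point holds as an inconsistency of thresholds. Table 7 is not exhaustive, and Section 13.3.6.1 uses two thresholds that its own scale does not contain. Applied as written, the Related row leaves out the possible and probable events that the table claims to count. Applied differently across investigators, the count has no single threshold. This rests on the text as translated and on Table 7 being the definition that investigators use.

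The size cannot be quantified. Three stronger readings should be resisted:

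- That related toxicity will certainly be understated. This follows only if the Related row is applied literally. The opposite error is possible, although it is the weaker case because Not Related excludes a *reasonable* relationship rather than any conceivable one.
- That the related-anemia rate is uncertain from 0 to 42.3%. The upper figure is the pooled incidence in Section 4.2.3 (879/2076 = 0.423, or 0.4234 × 82 = 34.7 patients if it applied here). A related rate can never exceed the all-cause rate, so this range holds under any definition and does not measure the defect.
- That late SAEs will be lost. *Suspected* and *considered* may be loose synonyms, and all reported SAEs are listed in any case. This is a wording point only.

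The related-TEAE table should be corrected. The primary analysis is not in question.

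**What to change.** 1. **Table 7.** Make the rows exhaustive and place the middle band on the side that matches the planned table. Related would mean a reasonable possibility that study treatment caused or contributed to the event, and Not Related would mean all other events. Check the word *definite* against the source-language text first.
2. **Section 13.3.6.1.** Label the table simply as related TEAEs. Replace the repeated-event rule with two: worst grade per patient and preferred term for the all-cause tables, and worst grade among related episodes for the related table.
3. **Late events.** Use the same relatedness term in Sections 12 and 13.3.6.1.
4. **Dose-modification passages.** Section 11.1.5, Table 6, Section 11.1.5.1 and Section 11.1.5.2 all depend on relatedness. The sponsor must reconcile them with the revised definition. No dose rule is proposed here.

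**Cost.** The changes are to wording in Table 7, Section 12, Section 13.3.6.1 and the eCRF completion guidance, plus the reconciliation in item 4. Reported related rates may shift. The protocol is already at version 4.0, so any events coded under the present wording must be re-attributed or reported as coded under it.
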